## 2.3 EXPLORATORY OBJECTIVES AND ASSOCIATED ENDPOINTS

Exploratory Objectives	Associated Exploratory Endpoints
1. Describe the efficacy of VGX-3100, administered alone or in combination with imiquimod, at Week 74 and/or Week 96 as measured by reduction in the surface area of vulvar lesion(s), in subjects without a complete resolution at Week 48	1. Percent reduction in the cumulative surface area of the acetowhite vulvar lesion(s) as determined by the quantitative analysis of standardized photographic imaging at Week 74 and/or Week 96 compared to baseline  . Results will be classified as: no clinically significant lesion resolution (reduction in lesion area of 0-25%), partial lesion area resolution (>25% and <100% reduction), and complete lesion resolution (no visible lesion).
2. Describe the efficacy of 5 or 6 doses of VGX-3100, alone or in combination with prior imiquimod, as measured by histologic regression of vulvar HSIL	2. Proportion of subjects with no evidence of vulvar HSIL on histology (i.e. biopsies or excisional treatment) at Week 74 for subjects who receive 5 doses of VGX-3100 and at Week 96 for subjects who receive 6 doses of VGX-3100.
3. Describe the efficacy of 5 or 6 doses of VGX-3100, alone or in combination with prior imiquimod, as measured by virologic clearance of HPV-16/18	3. Proportion of subjects with no evidence of HPV-16/18 in vulvar tissue samples at Week 74 and/or Week 96.
4. Evaluate tissue immune responses to VGX-3100, and VGX-3100 with imiquimod, as measured in vulvar tissue samples	4. Assessment of CD8 + and FoxP3 infiltrating cells  .
5. Describe virologic clearance of HPV-16/18 from other anatomic locations outside the vulva	5. Proportion of subjects who have cleared HPV-16/18 on specimens from other anatomic locations without surgical intervention (inclusive of cervix, oropharynx, vagina and intra-anus) at Week 48
6. Characterize HLA haplotypes and the correlation with efficacy	6. Proportion of subjects with regression of HSIL on histology (i.e. biopsies or excisional treatment) at Week 48 visit
7. Assess skin-to-muscle, skin-to-bone, and muscle thicknesses via ultrasound measure of deltoid (or quadriceps if applicable) and the correlation of needle depth into muscle with efficacy.	7. Ultrasound-measured skin-to-muscle, skin-to-bone, and muscle thicknesses.
8. Describe patient reported outcomes for subjects treated with VGX-3100 and VGX-3100 with imiquimod	8. Patient-reported outcome (PRO) endpoints will be obtained prior to first dose (Day 0), on the day of and following each of the first four doses, and at Weeks 48, 52, 74, 96 and 100.

 Digital photos will be analyzed with a computer program to calculate the total lesion size in cm^2.

 Additional assessments may include visualization of PD-L1, Granulysin, Perforin, CD137, CD103 and possibly other relevant markers identified in the literature in vulvar tissue as sample allows.

### 3. STUDY DESIGN

HPV-201 is a Phase 2, randomized, open-label efficacy study of VGX-3100 (DNA plasmids encoding E6 and E7 proteins of HPV types 16 and 18) administered by IM injection followed by EP delivered with CELLECTRA® 2000 alone or in combination with imiquimod in adult women with histologically confirmed vulvar HSIL associated with HPV-16/18. Approximately 36 subjects will be enrolled. Twenty-four subjects will receive VGX-3100 alone and 12 subjects will receive VGX-3100 and topical imiquimod treatment.

Subjects are randomized in a stratified manner according to (a) recurrent disease at screening (0 vs. 1 or more recurrences), (b) multifocal disease (1 vs. 2 or more lesions at screening), (c) Body Mass Index (BMI) category ( $\leq 25$  vs.  $> 25$  kg/m^2), and (d) age category ( $< 45$  years vs.  $\geq 45$  years).

To assess quality of life and related impacts on subjects, patient-reported outcome (PRO) instruments will be provided and will include the Short Form Health Survey version 2 (SF-36v2™), the EQ-5D-5L (EuroQol Research Foundation), and two additional PRO questions assessing quality of life after surgery or biopsy.

To be eligible for the study, subjects must consent to participate and have a minimum of a 4 mm vulvar punch biopsy/biopsies with lesion remaining, and photographs of the acetowhite vulvar lesion(s) at the time of screening. In the case of multifocal disease, the two regions of most advanced and severe disease, as judged by the investigator, should be chosen for biopsy using vulvoscopy and documented using standardized high resolution photography with a digital single-lens reflex (SLR) camera on the case report form. Biopsy slides or tissue will be sent to a Pathology Adjudication Committee (PAC) for evaluation prior to enrollment. In order to be eligible for enrollment, the PAC must assign the diagnosis of vulvar HSIL based on the biopsy sample(s). Subjects must also have a vulvar specimen test positive for HPV genotype 16 and/or 18 to be eligible for participation in the study.

The total duration of the study is up to 10 weeks for the screening period and 100 weeks for the treatment and follow-up periods.

#### 3.1 TREATMENT REGIMENS

All eligible subjects who consent to participate in the study will receive four doses of 6 mg of VGX-3100 administered by IM injection followed by EP. The first dose will be administered as soon as possible following confirmation of the HSIL diagnosis, HPV-16/18 status and all other eligibility criteria but no more than 10 weeks following collection of the subject's biopsy specimen used for diagnosis by the PAC.

Each dose of VGX-3100 will be administered in a 1 mL volume IM (deltoid, preferred site, or anterolateral quadriceps, alternate site) followed immediately by EP with the CELLECTRA® 2000 device. As shown in [Figure 1](#), study subjects will receive at least 4 doses of VGX-3100 and potentially a 5th and 6th dose depending upon their disposition with regard to histologic and lesion area changes. The first dose will be administered on Day 0, the second at Week 4, the third at Week 12, and the fourth dose will be administered at Week 24. Subjects with no HSIL at Week 48 (Subgroups A and B) will receive 4 doses. Subjects with HSIL at Week 48, who have a reduction in lesion size or no increase in lesion size from baseline (Subgroups C or D), may receive a fifth dose of VGX-3100 administered IM with EP at Week 52 per the judgment of the Investigator. Subjects with HSIL at Week 74, who have a reduction in lesion size or no increase in

lesion size from baseline (Subgroups C or D), may receive a sixth dose of VGX-3100 administered IM with EP at Week 78 per the judgment of the Investigator. Subjects in Subgroup E should receive surgical treatment per the judgement of the Investigator. All subjects will complete the study at Week 100.

Imiquimod treatment - Subjects randomized to the VGX-3100 with imiquimod arm will apply imiquimod 5% cream to the vulvar lesion beginning in the evening on Day 0, and will continue to apply treatment three times per week for 20 weeks (inclusive of administration in the evening of VGX-3100 dosing). Subjects unable to tolerate imiquimod treatment may reduce their dosing frequency, and will document their use on the imiquimod dosing log provided.

### 3.2 EFFICACY ASSESSMENT

The efficacy assessment will be based upon histopathology. Visualization of a normal appearing vulva by visual inspection with vulvoscopy is insufficient evidence to confirm disease regression. Disease regression will be based on histopathologic assessment at Week 48, 74 and 96. Subjects will be monitored during the course of the study by vulvoscopy. Lesion(s), defined as areas that stain acetowhite, will be assessed during vulvoscopy at Screening, Day 0, and Weeks 4, 12, 27, 48, 74 and 96 visits. Using standardized high resolution digital imaging, vulvar lesion(s) will also be quantitatively measured at Screening, Day 0, and Weeks 4, 12, 27, 48, 74 and 96.

Biopsies obtained as part of the study at Screening will be from the region of most advanced and severe disease as judged by the Investigator, and must be a minimum of 4 mm in length. Visible lesion must remain after screening biopsy to ensure measurement on study.

The decision process following results of the Week 48 biopsy are described in [Figure 2](#) and are as follows: At Week 48, the subject will undergo repeat vulvar punch biopsy/biopsies of the same lesion as study start, but adjacent to the original site within the boundaries of the original lesion (see [Table 3](#) for Minimally Required Biopsy Procedures). If after evaluation of biopsy tissue by the PAC there is no evidence of HSIL ([Figure 2](#), Subgroups A or B), the subject will continue to Week 74 for vulvoscopy, and biopsy adjacent to the site of initial biopsy.

If after evaluation of the biopsy tissue HSIL remains, but there is a reduction in lesion size or no increase in lesion size from baseline ([Figure 2](#), Subgroups C or D), the Investigator has the option to give the subject a 5th dose of VGX-3100 at Week 52, and the subject will continue on study with vulvoscopy and biopsy at Week 74. Alternatively, the Investigator may choose to treat the subject with surgical or standard treatment, and the subject will continue on study without further biopsy.

The decision process following results of the Week 74 biopsy are described in [Figure 3](#) and are as follows: At Week 74, the subject will undergo repeat vulvar punch biopsy/biopsies of the same lesion as study start, but adjacent to the original site within the boundaries of the original lesion (see [Table 3](#)). If after evaluation of biopsy tissue by the PAC there is no evidence of HSIL (Subgroups A or B), the subject will continue to Week 96 for vulvoscopy, and biopsy adjacent to the site of the initial biopsy.

If HSIL remains but there is a reduction in lesion size or no increase in lesion size from baseline (Subgroups C or D), the Investigator has the option to give the subject a 6th dose of VGX-3100 at Week 78, and the subject will continue on study with vulvoscopy and

biopsy at Week 96. Alternatively, the Investigator may choose to treat the subject with surgical or standard treatment, and the subject will continue on study without further biopsy.

The decision process following results of the Week 74 biopsy are as described in [Figure 4](#) and are as follows: At Week 96, the subject will undergo repeat vulvar punch biopsy/biopsies of the same lesion as study start, but adjacent to the original site within the boundaries of the original lesion (see [Table 3](#)). If there is no vulvar HSIL (Subgroups A or B), no further procedures are required. If after evaluation of biopsy tissue by the PAC there is vulvar HSIL (Subgroups C or D), or worsening disease (Subgroup E), the subject will receive surgical or other standard treatment.

In the event of worsening disease (ie, Subgroup E - any increase in lesion area from baseline or worsening of HSIL to cancer), the subject will receive surgical treatment per the Investigator's judgement and will continue on study through Week 100 with vulvoscopy, but without further biopsy. For a finding of carcinoma, subjects will receive surgical treatment, and be discontinued from study treatment. The event will be reported as an SAE per [section 7.1.4](#). If wide excision is required, the sample obtained will be sent to the PAC for evaluation.

Pre-biopsy Vulvoscopy Finding	Minimally required procedure
No acetowhite lesion	Vulvar punch biopsy and imaging; biopsy should be conducted of the same lesion as study entry, but adjacent to the original biopsy site within the boundaries of the original lesion;
Acetowhite Lesion	Vulvar punch biopsy and imaging; biopsy should be conducted of the same lesion as study entry, but adjacent to the original site within the boundaries of the original lesion; biopsy of lesion must include suspected area of most advanced disease
Multiple acetowhite lesions	Vulvar punch biopsies and imaging; biopsy should be conducted of the same two lesions as study entry but adjacent to the original site within the boundaries of the original lesion; biopsies must include area of most advanced and severe disease as determined at screening

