## 6.12 VULVAR HPV TESTING

A 4 mm vulvar punch biopsy sample will be obtained at Screening, Weeks 48, 74, and 96, and will be sent to a central laboratory for HPV genotyping by PCR. In the case of multifocal disease, a 4 mm vulvar biopsy will be obtained from two regions of most advanced and severe disease as judged by the investigator. The subject will be requested to abstain from sexual activity and refrain from use of douching vulvar biopsy samples to eliminate potential interference with the results of HPV testing.

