### 8.3 SAMPLE SIZE/POWER

A sample of 36 subjects will be randomized to receive either 6 mg VGX-3100 or 6 mg VGX-3100 plus imiquimod, IM followed by EP in a 2:1 ratio. This sample size provides 80% power to declare each arm superior to historical control, assuming the true proportion of subjects who achieve the primary endpoint is 20% and 28% for the respective treatment arms and 2% for the historical control, and that 90% are evaluable at Week 48 from randomization.

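### Table 3 lets that day's vulvoscopy set the minimum number of follow-up biopsies while section 6.12 asks for two regions in multifocal disease; under Table 3 alone a woman with two entry lesions can be a responder with one never re-sampled

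*Protocol*

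**What the plan says.** At entry, section 3 has a woman with multifocal disease biopsied in two regions, and section 6.14 speaks of two lesions. For Week 48 the text of section 3.2 gives no number of samples and refers to Table 3 for the minimum.

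Table 3 chooses the procedure by the vulvoscopy finding immediately before the biopsy:

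- Nothing acetowhite on the day: "Vulvar punch biopsy and imaging; biopsy should be conducted of the same lesion as study entry, but adjacent to the original biopsy site".
- One acetowhite lesion: again one biopsy of the entry lesion, with the added condition "biopsy of lesion must include suspected area of most advanced disease".
- Multiple acetowhite lesions: biopsies of the same two lesions as at entry. This is the only row that asks for two.

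Section 6.12 covers the tissue taken at Screening and at Weeks 48, 74 and 96. It says that in multifocal disease "a 4 mm vulvar biopsy will be obtained from two regions of most advanced and severe disease as judged by the investigator". That wording stands in versions 1.0 and 1.1. The version 1.2 text at hand stops at the heading of 6.12, and the summary of changes for version 1.2 lists no change to that section.

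Section 3.2.1 defines a responder by the absence of HSIL and of HPV-16/18 in the vulvar tissue evaluated, with no non-study medication for the lesions. It does not require tissue from every lesion biopsied at entry.

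**The concern.** Histology and HPV PCR on this tissue decide the whole primary endpoint, so the number of sites sampled is part of the endpoint definition. Under Table 3 that number falls as the vulva looks better. A woman biopsied in two lesions at entry, with none or one still acetowhite at Week 48, meets the minimum with one sample. If that sample is clear she counts as a responder, and the other entry lesion is taken as cleared on its appearance.

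The error has one direction. Leaving a lesion out can hide residual HSIL or HPV; it cannot turn a true responder into a non-responder. Section 6.12 points the other way for the same woman at the same visits, so a site can follow Table 3 in good faith and collect less tissue than 6.12 asks for. Tissue not taken at Week 48 cannot be recovered at analysis.

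**Working it through.** **Passages side by side.** Take a woman with two lesions biopsied at entry.

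| Lesions acetowhite at Week 48 | Minimum under Table 3 | Section 6.12, multifocality read as at screening |
|---|---|---|
| Two | Both entry lesions | Two regions |
| One | One biopsy | Two regions |
| None | One biopsy | Two regions |

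The passages agree in the first row and differ in the other two. Section 6.12 does not itself say when multifocality is judged. The only dated definition is the stratification factor in sections 3 and 8.2, which counts lesions at screening.

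**How many responders decide an arm.** Inputs: 24 and 12 women (section 3); an exact one-sided test at 0.025 against 2%, each arm separately (section 8.9); and, from section 8.3, assumed response rates of 20% on VGX-3100 alone and 28% with imiquimod. The reference rate and the evaluable share are given there as "2% for the historical control, and that 90% are evaluable at Week 48 from randomization".

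Evaluable women: 0.9 × 24 = 21.6, so 21 or 22; 0.9 × 12 = 10.8, so 10 or 11.

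The plan's own figure comes first: "This sample size provides 80% power to declare each arm superior to historical control". The threshold r is the smallest count with P(X ≥ r | n, 0.02) < 0.025.

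- VGX-3100 alone, n = 22: r = 3. Power = 1 − 0.8^22 − 22(0.2)(0.8^21) − 231(0.2^2)(0.8^20) = 84.6% (82.1% at n = 21).
- With imiquimod, n = 11: r = 2. Power = 1 − 0.72^11 − 11(0.28)(0.72^10) = 85.8% (81.7% at n = 10).

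The stated 80% is met as a floor in both arms.

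**Removing one responder at the threshold.**

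| Result | One-sided p against 2% | 95% Clopper-Pearson lower bound | Superior? |
|---|---|---|---|
| 3/22 | 0.0093 | 2.9% | Yes |
| 2/22 | 0.071 | 1.1% | No |
| 2/11 | 0.0195 | 2.3% | Yes |
| 1/11 | 0.199 | 0.2% | No |

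At n = 21 and n = 10 the thresholds are still 3 and 2.

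**Illustration on assumed values.** The documents give neither the multifocal share nor the residual disease in faded lesions. Let m be the share of women with two or more lesions, and q the chance that a multifocal non-responder is counted as a responder because the affected entry lesion was not re-sampled. If the true rate is 2%, the apparent rate is 0.02 + 0.98 × m × q.

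| m, q (assumed) | Apparent rate | P(X ≥ 3), n = 22 | P(X ≥ 2), n = 11 |
|---|---|---|---|
| No misclassification | 2.0% | 0.009 | 0.020 |
| 25%, 2% | 2.5% | 0.017 | 0.029 |
| 25%, 5% | 3.2% | 0.033 | 0.047 |
| 50%, 5% | 4.5% | 0.072 | 0.083 |
| 50%, 10% | 6.9% | 0.191 | 0.173 |

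The chance of a false success runs from below the nominal 0.025 to several times it. This shows sensitivity to the assumptions and is not an estimate.

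**The case against.** The strongest reply is that Table 3 is only a minimum and 6.12 sets the higher requirement. Taking two samples satisfies both. With multifocality read as at screening, 6.12 still applies to a woman whose lesions have faded, and a site that takes one sample is not complying. This largely stands, and it makes the point one of reconciliation. It does not dispose of it: section 3.2 sends the site to Table 3 for the Week 48 biopsy, 6.12 neither dates multifocal status nor says that the two regions are the two entry lesions, and 3.2.1 would still accept the woman as a responder.

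It can also be said that the sentence "Visualization of a normal appearing vulva by visual inspection with vulvoscopy is insufficient evidence to confirm disease regression" only bars declaring regression without histology, and that Table 3 honours it by requiring a biopsy even when nothing is visible. That is fair; the sentence does not fix a number of samples. For the lesion left out, though, appearance is the only evidence.

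Three stronger readings are tempting and not supported:

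- That the response rate is overstated by a stated number of points. This needs the residual risk in a faded lesion and the correlation between lesions in one woman. The documents give neither, and lesions sharing one systemic treatment may well clear together.
- That the multiple-lesion row biases the result because "biopsies must include area of most advanced and severe disease as determined at screening". Returning to the area that was worst at screening gives a paired before-and-after sample and is a defensible choice.
- That sites will in practice measure different endpoints. The passages allow this; they do not show that it will happen.

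Finally, one responder deciding an arm follows from the small arms and holds for any misclassification. It shows why small errors matter here, not how often this one occurs.

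**Conclusion.** The point holds as a conflict between two instructions for collecting the primary-endpoint tissue. It affects women with two lesions biopsied at entry of whom none or one is still acetowhite at follow-up. Under Table 3 alone such a woman can be a responder with one entry lesion never re-sampled, and the resulting bias can only favour response.

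Its size cannot be derived, because the multifocal share, the residual disease and the between-lesion correlation are not given. What can be said is that the thresholds are 3 of 22 and 2 of 11, so a single such woman can change an arm's conclusion. The conflict with 6.12 rests on version 1.1 text carrying over into version 1.2, which the summary of changes suggests but which cannot be confirmed here. The gap inside Table 3 and section 3.2.1 is in version 1.2 itself. A reader might infer that the design is invalid or the power claim wrong; neither follows. This is a clarification worth making before Week 48 visits.

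**What to change.** Reconcile Table 3 with 6.12 so that the number of follow-up samples is set by the lesions biopsied at entry, with multifocality as at screening, whatever vulvoscopy shows on the day. Use the same wording in both places for Weeks 48, 74 and 96, wherever a biopsy is still due.

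In section 3.2.1, state that responder status requires tissue from each lesion biopsied at entry. If the sponsor prefers not to add a condition to the endpoint, given that section 8.11.6 rules out imputing missing data, the least that is needed is a prespecified sensitivity analysis counting women with an un-resampled entry lesion as non-responders, with their number reported by arm.

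The cost is a rewording of Table 3 and a sentence in 3.2.1. No sample is added beyond what 6.12 already calls for in multifocal disease. The observed response rate may be slightly lower.

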### 3.2.1 DEFINITION OF RESPONDER AND NON-RESPONDER

Responder and non-responder definitions ([Table 4](#)) take into account both histopathologic regression of vulvar HSIL and virologic (HPV-16/18) clearance from tissue samples since HPV persistence is an important factor in the clinical progression of HSIL.

A treatment responder is defined as a subject with no histologic evidence of vulvar HSIL and no evidence of HPV-16 or HPV-18 in vulvar tissue at evaluation and who did not receive non-study related medication for treatment of VIN lesions. A treatment non-responder is a subject with histologic evidence of vulvar HSIL, adenocarcinoma-in-situ, or vulvar carcinoma at evaluation, and/or a subject with evidence of HPV-16/18 at evaluation, or a subject who received non-study related medications for treatment of VIN lesions. Any

case of histologically confirmed progression is considered a non-responder. Progression is defined as advancement to carcinoma by histology.

Table 4: Definition of Responder and Non-responder	
Responder	Non-Responder
Subject with no histologic evidence of vulvar HSIL a AND Subject with no evidence of HPV-16 or HPV-18 in vulvar tissue at evaluation AND Subject who did not receive non-study related medication for treatment of VIN lesions.	Subject with histologic evidence of vulvar HSIL, Adenocarcinoma-in-situ (AIS), vulvar carcinoma at evaluation  AND/OR Subject with evidence of HPV-16 or HPV-18 in vulvar tissue at evaluation  OR Subject who received non-study related medication for treatment of VIN lesions

### 3.3 SAFETY ASSESSMENT

Safety monitoring will include:

- 1) Local and systemic events for 7 days following each dose as noted in the Participant Diary
- 2) All adverse events including SAEs, SUSARs, UADEs, and other unexpected AEs for the duration of the study.

All subjects will be followed for 100 weeks.

